Protocol:

A randomized placebo controlled trial of inhaled beclomethasone after community-acquired respiratory viral infection in lung transplant recipients

Version: 5

Date: 5.28.15

1. Abstract

The randomized placebo controlled trial of inhaled beclomethasone after community-acquired respiratory viral (CARV) infection in lung transplant recipients is a single center pilot study evaluating the impact of inhaled beclomethasone on the development and progression of chronic lung allograft dysfunction (CLAD) or death after CARV infection. The study will randomize 40 subjects to inhaled beclomethasone or placebo in a 1:1 ratio, and follow-up will be complete 12 months after randomization. The primary objective of the study is to determine if inhaled beclomethasone has greater efficacy than placebo for the endpoint of CLAD development or progression or death after randomization. The study will also assess multiple secondary endpoints including the safety and tolerability of inhaled beclomethasone in lung transplant recipients, respiratory viral symptom scores, the development of donor-specific human leukocyte antigen antibodies and antibodies to lung-specific self-antigens, and survival.

2. Background

Lung transplantation is the ultimate treatment for patients with advanced lung disease. However, long-term outcomes remain disappointing, and the median survival after transplantation is approximately 5.5 years. While infection and graft failure are the leading causes of death in the first year after transplantation, chronic rejection is the leading cause of death beyond the first year. Chronic rejection after lung transplantation is characterized histologically as obliterative bronchiolitis, although histologic confirmation is difficult. Therefore, chronic lung allograft syndrome (CLAD) and bronchiolitis obliterans syndrome (BOS), defined and staged based on changes in spirometry measurements, are the clinical surrogates of chronic rejection after lung transplantation. The incidence of CLAD approaches 50% at 3 years after transplantation, and there is no effective evidence-based treatment. Unfortunately, this results in a progressive and relentless decline in lung function culminating in graft failure and death. Indeed, the median survival after the diagnosis of CLAD is 3 years, and studies have consistently demonstrated a significantly reduced quality of life in patients with CLAD. Clearly, CLAD is the leading obstacle to better outcomes after lung transplantation, and lung allograft recipients urgently need strategies to prevent or delay the onset of CLAD.

The pathophysiology of CLAD has not been elucidated, but clinical risk factors have been identified and these provide insights into the underlying immunobiology. Studies have consistently identified episodes of acute rejection, lymphocytic bronchiolitis, primary graft dysfunction, donor-specific HLA antibodies (DSA), gastroesophageal reflux disease, and community-acquired respiratory viral (CARV) infections as independent risk factors for the development of CLAD. The exact mechanisms whereby CARV infection increases the risk of CLAD are unclear, but this association has been identified in both upper and lower respiratory tract infections. We have proposed that viral infection results in airway epithelial cell injury and the expression of injury-response genes that provide signals that initiate immunologic and non-immunologic pathways that result in the airway remodeling characteristic of obliterative bronchiolitis. In addition, CARV infection may increase the expression of HLA molecules in the allograft and expose cryptic self-antigens while creating the necessary inflammatory milieu for CLAD development and progression.

Systemic and inhaled corticosteroids are frequently used as anti-inflammatory agents to treat the peribronchiolar inflammation seen in viral bronchiolitis. Beneficial effects from corticosteroids have been reported, but this has not been demonstrated in lung transplant recipients.

The aim of this single center, randomized, double blind, placebo controlled study is to evaluate the short and long term effects of a 6 month course of inhaled beclomethasone on adult lung transplant recipients with CARV infection.

3. Transplant Center Experience

The study center (Barnes-Jewish Hospital / Washington University) has performed lung transplants (LTx) in over 1300 recipients since 1988. This center has long-term experience in evaluating and selecting candidates, performing transplantation, and providing high-quality follow-up. Post-transplant survival outcomes at this center are higher than the national average.

4. Study Protocol

4.1. Primary Aim

To conduct a single center, pilot, randomized placebo controlled trial that compares the efficacy and safety of inhaled beclomethasone versus placebo to prevent the development or progression of CLAD, or death after CARV infection in lung transplant recipients.

4.2. Hypotheses

Null Hypothesis There is no difference in incidence of new or progressive CLAD, or death between the two randomized treatment groups (placebo = inhaled beclomethasone)

Alternative There is a statistically significant difference in the incidence of new or progressive CLAD, or death between the two randomized treatment groups (placebo ≠ inhaled beclomethasone)

4.3. Study Objectives

Primary Objective

- To determine if inhaled beclomethasone has greater efficacy than placebo in preventing the composite endpoint of new or progressive CLAD or death 6 months after CARV infection in adult lung transplant recipients.

Secondary Objectives

- Incidence of new or progressive CLAD at 6 and 12 months after CARV infection
- Time to development or progression of CLAD
- Safety and tolerability of inhaled beclomethasone
- Respiratory viral symptoms
- Development of donor-specific HLA antibodies (DSA)
- Change in DSA mean fluorescence intensity
- Development of antibodies to lung-specific self-antigens (Collagen V and K- α 1 tubulin)
- Serum cytokine profiles
- Peripheral immune cell phenotypes
- Incidence of other bacterial, viral, or fungal infection at the time of CARV infection
- Incidence of acute rejection and lymphocytic bronchiolitis within 6 months following CARV infection
- Survival at 6 months (+ 10 days) and 12 months (+ 10 days) after CARV infection

4.4. Design

Single center, double blind, placebo controlled randomized trial

4.5. Setting

This single center trial will enroll 40 patients from Washington University School of Medicine and Barnes-Jewish Hospital academic lung transplant center. Screening, participant consent, treatment, and data collection will be conducted at this transplant center.

4.6. Study Population and Eligibility Criteria

The study staff will prescreen/screen all lung transplant (LTx) recipients at the institution who develop respiratory symptoms suggestive of a CARV infection. The study will only enroll a patient if he/she can come to the medical center to receive study drug. In general, the study staff will consent patients who have undergone lung transplantation, and randomize study participants (consented patients) that develop post-transplantation CARV infection. Table 1 outlines specific study eligibility criteria for enrollment and randomization. A screening log will document limited information regarding patients that undergo screening but not enrollment. Case report form (CRF)/computer data entry system will capture reason(s) for exclusion.

Table 1. Eligibility criteria for enrollment in the study

Inclusion Criteria:

- Adult (≥ 18 years old)
- Single, bilateral, or heart-lung transplant recipient
- Confirmed infection with a community-acquired respiratory virus
 - Including: adenovirus, coronavirus, influenza A or B, respiratory syncytial virus (RSV), parainfluenza virus (PiV), human metapneumovirus (hMPV), and rhinovirus/enterovirus
- At least 6 months post-transplant, with completion of 6 month surveillance bronchoscopy if indicated
- Able and willing to give written informed consent and comply with study procedures (e.g. testing, treatment)
- Able to undergo randomization and initiate study drug within 10 days of CARV infection

Exclusion Criteria:

- BOS Stage 3 [pre-CARV baseline $FEV_1 < 50\%$ of personal reference]
 - Pre-CARV baseline: the average of the 2 most recent FEV_1 separated by at least 3 weeks and also occurring within the 6 months prior to the CARV infection
 - In the event that only a single FEV_1 is available within the previous 6 months, that value will function as the pre-CARV baseline
 - Personal reference: the average of the 2 highest post-transplant FEV_1 at least 3 weeks apart
- Requirement for mechanical ventilation at study entry
- Use of inhaled steroids at the time of CARV infection
- Any condition that in the investigator's opinion would preclude the patient's participation in a clinical trial
- Lack of available spirometric data within 6 months preceding CARV infection to establish a baseline FEV_1 and/or FVC
- Pregnancy
- Current participation in another interventional clinical trial

4.7. Sampling Design

The study staff will assess all LTx recipients with a CARV infection for enrollment.

4.8. Randomization

Eligible patients who develop a CARV infection after lung transplantation will need to provide written informed consent prior to study participation and will undergo randomization using a computer-generated method with a 1:1 ratio, and stratified by BOS stage (group 1: BOS stages 0 and 0p vs. group 2: BOS stages 1 and 2) to one of the treatment assignments: (1) inhaled beclomethasone, or (2) placebo. The site will aim to randomize patients within 7 days of identification of CARV infection.

4.9. Endpoints

4.9.1. Composite Primary Endpoint

Freedom from new or progressive CLAD, or death 180 days after CARV infection.

4.9.2. Secondary Endpoints

Incidence of new and/or progressive CLAD, safety and tolerability of inhaled beclomethasone, respiratory virus symptom score, development of DSA, change in DSA mean fluorescence intensity, development of antibodies to

self-antigens, serum cytokine profiles, peripheral immune cell phenotypes, incidence of other bacterial, viral, or fungal pulmonary infections at the time of CARV infection, incidence of acute rejection and lymphocytic bronchiolitis within 6 months (+ 10) days after CARV infection, incidence of new or progressive CLAD within 12 months (+ 10) after CARV infection, and survival 6 months (+ 10 days) and 12 months(+ 10 days) after CARV infection.

4.10. Outcomes Assessment

The development of CLAD is defined according to the following criteria:

- CLAD: FEV_1 and/or $FVC \leq 80\%$ baseline on 2 measurements obtained 3 weeks apart

Once CLAD has been established, it will be further defined by the following criteria:

- Restrictive CLAD (RAS): $FVC \leq 80\%$ baseline on 2 measurements obtained 3 weeks apart with an FEV_1/FVC ratio $\geq 75\%$
- Obstructive CLAD (BOS): $FEV_1 \leq 80\%$ baseline on 2 measurements obtained 3 weeks apart

Progressive CLAD is defined as a $\geq 15\%$ decrement in pre-CARV infection baseline FEV_1 or FVC . The pre-CARV infection baseline FEV_1 and FVC are defined as the average of the 2 most recent FEV_1 or FVC measurements separated by at least 3 weeks, and occurring within the 6 months prior to the diagnosis of the CARV infection. In the event that only 1 FEV_1 or FVC measurement is available in the previous 6 months, that value will serve as the pre-CARV infection baseline FEV_1 or FVC .

5. Treatments

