5.3. Immunosuppression

Patients' induction and maintenance immunosuppression will be prescribed and managed according to our transplant program's standard clinical practice. Likewise, we will treat and manage acute rejection, lymphocytic bronchiolitis, and BOS according to our standard clinical practice.

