6.3. Bronchoscopy

Bronchoscopy will only be performed if clinically indicated. Surveillance bronchoscopy to evaluate for occult acute rejection is performed at 1, 2, 3, 6, and 12 months after transplantation based on our clinical practice. In addition, bronchoscopy is performed to evaluate respiratory symptoms or clinical signs of allograft dysfunction (e.g.,

hypoxemia, pulmonary infiltrates, clinically significant decrements in spirometry). Bronchoscopy will not be performed for study reasons only.

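### Section 4.10 scores CLAD on the size of the spirometric fall alone, so a fall explained by another treatable episode can enter the primary endpoint, most easily as progressive CLAD

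*Combined protocol and SAP*

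**What the plan says.** The primary endpoint in section 4.9.1 is "Freedom from new or progressive CLAD, or death 180 days after CARV infection". Section 4.10 is the only place that defines CLAD. It begins "The development of CLAD is defined according to the following criteria", and it has two rules:

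- New CLAD: FEV1 and/or FVC at or below 80% of "baseline on 2 measurements obtained 3 weeks apart".
- Progressive CLAD: at least a 15% "decrement in pre-CARV infection baseline FEV_1 or FVC". No second measurement is mentioned.

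Neither rule has a condition on cause, recovery or response to treatment. No section provides for endpoint adjudication or sets aside readings taken around another diagnosed episode.

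Elsewhere the protocol keeps acute rejection and lymphocytic bronchiolitis apart from CLAD. Section 2 lists both as risk factors for it. Section 4.3 has its own secondary objective, "Incidence of acute rejection and lymphocytic bronchiolitis within 6 months following CARV infection", over essentially the same window as the primary endpoint. Section 5.3 says "we will treat and manage acute rejection, lymphocytic bronchiolitis, and BOS according to our standard clinical practice". Section 6.3 says "bronchoscopy is performed to evaluate respiratory symptoms or clinical signs of allograft dysfunction" and gives spirometric decline as one example of such a sign. Section 6.2 adds unscheduled spirometry when new symptoms or infiltrates appear.

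**The concern.** Two kinds of spirometric loss can meet the rules in section 4.10: the chronic loss that the trial is about, and a fall during a separate episode later in follow-up that may recover. The site will often know that another cause was found, but that knowledge has no role in scoring. Because section 6.2 adds spirometry at times of acute illness, such falls are likely to be measured.

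This matters because the test drug is an inhaled anti-inflammatory steroid, and section 2 gives peribronchiolar inflammation as the reason for using such drugs. It could plausibly change reversible inflammatory falls without changing chronic rejection, and the difference would then be read as an effect on CLAD. If it leaves those falls unchanged, they add events to both arms and shrink the difference.

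It may also be hard to repair afterwards. Sections 4.3 and 4.9.2 count other infections only at the time of the index viral infection, and section 8.4.2 specifies CRF collection for serious adverse events. A later, non-serious infection that lowers FEV1 has no specified place on the CRF.

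**Working it through.** **What gets through each rule**

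| Situation during follow-up | New CLAD | Progressive CLAD |
|---|---|---|
| Fall recovers before a second reading 3 weeks later | not counted | counted, one reading is enough as written |
| Fall with another documented cause, still present 3 weeks later | counted | counted |
| Lasting chronic loss | counted | counted |

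The two-reading condition is a real but partial safeguard for new CLAD. The progressive rule has none. Progression presumably concerns participants who enter with BOS stage 1 or 2 (the second stratum in section 4.8); the documents do not say how many are expected.

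**Reference power**

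Inputs: 40 participants randomised 1:1, so 20 per arm (section 1); 50% on placebo and an absolute reduction of 25 points (section 7); chi-squared test (section 7); two-sided alternative (section 4.2). Alpha is not stated; 0.05 is assumed.

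Exact power is the sum, over all pairs (x, y) for which the uncorrected chi-squared p-value is at most 0.05, of Bin(x; 20, p1) × Bin(y; 20, p2). For 50% versus 25% this is 37.5%. The normal approximation with pooled variance gives 36.8%. Section 7 states 80%, which does not reproduce. That shortfall is a separate matter; here 37% is only the starting point.

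**Dilution: same rate of non-CLAD falls in both arms**

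Let q be the share of otherwise event-free participants whose fall meets the rule for another reason. The observed rate is p + (1 − p)q, and the difference shrinks by the factor (1 − q). The documents give no value of q, so a range is shown.

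| q | Placebo | Beclomethasone | Difference (points) | Exact power |
|---|---|---|---|---|
| 0 | 50% | 25% | 25 | 37.5% |
| 5% | 0.50 + 0.50 × 0.05 = 52.5% | 0.25 + 0.75 × 0.05 = 28.75% | 23.75 | 32.5% |
| 10% | 0.50 + 0.50 × 0.10 = 55% | 0.25 + 0.75 × 0.10 = 32.5% | 22.5 | 28.3% |
| 20% | 0.50 + 0.50 × 0.20 = 60% | 0.25 + 0.75 × 0.20 = 40% | 20 | 22.2% |

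The planned 50% may already include such falls. True placebo CLAD is then (0.50 − q)/(1 − q). If the drug halves it and leaves q alone, the observed rates are 50% versus 27.5%, 30% or 35% for q of 5%, 10% or 20%. Power by the normal approximation is 30%, 25% or 16%, against 36.8% at q = 0.

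**Misattribution: the drug changes only the reversible falls**

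Assume true CLAD of 25% in both arms and reversible falls in 30% versus 10% of the rest. The endpoint reads 0.25 + 0.75 × 0.30 = 47.5% versus 0.25 + 0.75 × 0.10 = 32.5%. That is an apparent 15-point difference with no difference in CLAD. The chance of a significant result favouring the drug is about 15.5%.

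**The case against.** Section 2 says that CLAD and BOS are defined and staged by spirometry and serve as surrogates for chronic rejection. An any-cause rule is objective, needs no judgement, and suits a 40-patient pilot. A cause-based rule makes scoring depend on which episodes are detected clinically, since section 6.3 rules out bronchoscopy for study reasons alone. If the drug changes symptoms, it could change who is investigated. This stands as a real cost, and is why the any-cause rule should be kept as a sensitivity analysis.

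A reader might infer that every episode of rejection, lymphocytic bronchiolitis or infection is scored as CLAD. The documents do not support that. An episode must produce a fall of the required size, and for new CLAD the fall must be present on both readings.

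A reader might also object that one episode can count in both the primary endpoint and the rejection endpoint. That is not an error: the endpoints are analysed separately, and one participant may properly contribute to both.

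The rates used above are assumptions. In particular, nothing in the documents supports 30% versus 10%. The figures show a mechanism and its scale, and do not predict this trial's result.

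**Conclusion.** The point holds as a weakness in the endpoint definition. It rests on the wording of section 4.10 and on the absence of any condition elsewhere, not on an assumed rate. As written, the primary endpoint can include falls from treatable episodes that the protocol itself distinguishes from CLAD. For new CLAD only falls that outlast the 3-week interval get through; for progressive CLAD a single low reading suffices.

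The size cannot be derived from the documents. Under equal rates of 5% to 20% in both arms, power falls from 37% to between about 33% and 22%. Unequal rates could bias the contrast either way.

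A reader might go further and conclude that the trial would report that the drug prevents CLAD when it does not. The documents do not support that: even in the misattribution illustration a significant result favouring the drug has only about a 15.5% chance. The likelier harm is a misleading estimate.

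**What to change.** Change endpoint scoring in section 4.10 only; care is unaffected.

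1. Require the progressive-CLAD decrement to be confirmed on a second reading at least 3 weeks later.
2. For either rule, when a qualifying fall coincides with a documented episode of rejection, lymphocytic bronchiolitis or new infection, count it only if it is still present on a reading at least 3 weeks after the end of that episode as recorded on the CRF.
3. Date a confirmed event at the first qualifying reading. For a fall before day 180, let the confirming reading come from the spirometry already scheduled to month 12 (section 6.2). Count a fall that cannot be confirmed as an event.
4. Record such episodes, with start and end, on the CRF throughout follow-up while blinded.
5. Report the any-cause rule as a sensitivity analysis.

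The cost is a few sentences in section 4.10 and one added CRF item, which must also cover later infections because the current plan does not collect them. Some events will be confirmed later, and scoring will depend partly on clinically detected episodes; the any-cause analysis checks how much that matters.

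### The 80% rule for new CLAD does not name its reference, and the 15% rule for progressive CLAD needs no confirming measurement, so the primary endpoint is not fully defined.

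*Combined protocol and SAP*

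**What the plan says.** The primary endpoint (Section 4.9.1) is freedom from new or progressive CLAD, or death, at 180 days. Section 4.10 supplies the two spirometric rules.

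- New CLAD: "CLAD: FEV_1 and/or $FVC \leq 80\%$ baseline on 2 measurements obtained 3 weeks apart". The obstructive and restrictive subtypes also use an unqualified baseline ("baseline on 2 measurements obtained 3 weeks apart").
- Progression: "Progressive CLAD is defined as a $\geq 15\%$ decrement in pre-CARV infection baseline FEV_1 or FVC". This sentence names its reference but states no second measurement.
- Section 4.10 goes on to define that reference: "The pre-CARV infection baseline FEV_1 and FVC are defined as the average of the 2 most recent FEV_1 or FVC measurements", taken within the 6 months before diagnosis.

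Section 4.6 holds a second FEV1 standard: "Personal reference: the average of the 2 highest post-transplant FEV_1 at least 3 weeks apart". It is used to grade disease at entry: "BOS Stage 3 [pre-CARV baseline $FEV_1 < 50\%$ of personal reference". No FVC counterpart is given. Section 4.8 enrols patients with and without BOS and randomizes them "stratified by BOS stage (group 1: BOS stages 0 and 0p vs. group 2: BOS stages 1 and 2".

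**The concern.** New CLAD is one of three ways to reach the primary endpoint, and nothing states which reference its 80% line is drawn from. A patient whose lung function was already below its best before the infection can be an event on one reading and a non-event on the other, with identical measurements. Leaving this open also leaves room to settle it after the data are seen.

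The progression rule has a different weakness. One low test is enough, whereas new CLAD needs two tests 3 weeks apart. Repeated testing then gives ordinary measurement variation several chances to produce an event.

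The trial is small. At the planned rates in Section 7 (50% and 25%, taking 20 per arm) about 20 × 0.50 + 20 × 0.25 = 15 events are expected, and each reclassified patient moves an arm's rate by 1/20 = 5 percentage points.

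**Working it through.** **The reference.** Let r be pre-CARV FEV1 divided by personal reference. The fall from the pre-CARV level needed for new CLAD is:

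- pre-CARV reading: 20% for every r;
- personal-reference reading: 1 − 0.80/r.

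| r | pre-CARV reading | personal-reference reading |
|---|---|---|
| 1.00 | 20.0% | 20.0% |
| 0.95 | 20.0% | 15.8% |
| 0.90 | 20.0% | 11.1% |
| 0.85 | 20.0% | 5.9% |
| 0.82 | 20.0% | 2.4% |

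Two worked cases, both with r = 0.85:

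- A lasting fall from 85% to 69% of personal reference is 1 − 0.69/0.85 = 18.8%. On the pre-CARV reading this is not new CLAD, although FEV1 has crossed 80% of the standard used to grade BOS at entry.
- In litres, take a personal reference of 3.00 L and a pre-CARV value of 2.55 L. The new-CLAD line is 0.80 × 2.55 = 2.04 L or 0.80 × 3.00 = 2.40 L. A confirmed 2.30 L (a 9.8% fall) is an event on one reading only.

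**Confirmation of progression.** The documents give no within-patient variation, so I assume a CV of 5-7%, independent errors, a truly stable patient, and a pre-CARV baseline that is the mean of two tests. Section 6.2 plans spirometry every 1-2 months, hence three to six tests by day 180.

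Per test, a chance 15% fall means that the value is at or below 0.85 × baseline. The difference has mean 0.15 and SD = CV × √(1 + 0.85²/2) = 1.167 × CV.

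- CV 5%: z = 0.15/0.0583 = 2.57, probability about 0.5% per test, so about 3% over six tests and 1.5% over three.
- CV 7%: z = 0.15/0.0817 = 1.84, probability about 3.3% per test. Treating tests as independent gives 1 − 0.967⁶ ≈ 18% over six tests. The shared baseline makes tests correlated, and simulation (200,000 patients per case) gives about 16% over six tests and 9% over three.

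If two consecutive qualifying tests are required, the simulated probability is at most 1.4%.

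**Chance new CLAD by reference.** Same model, event confirmed on two consecutive tests, three to six tests, CV 5-7%:

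| r | personal-reference reading | pre-CARV reading |
|---|---|---|
| 0.82 | 17-44% | at most 0.1% |
| 0.85 | 3-17% | at most 0.1% |
| 0.90 | at most 1.5% | at most 0.1% |

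**Sensitivity of the result.** By uncorrected chi-squared, 10/20 against 5/20 gives p = 0.10. Moving one patient, to 10/20 against 4/20, gives p = 0.047.

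**The case against.** The text is less open than two definitions suggest. Only the pre-CARV baseline is defined for FVC, and the Section 4.6 exclusion for missing spirometry uses an unqualified baseline for the 6-month pre-CARV value. That stands: the pre-CARV reading is the more natural one. It is still not stated, and it sits awkwardly beside BOS staging at entry. The explicit tie to the personal reference is for stage 3; that the strata use the same standard is an inference.

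A reader might infer that the plan is illogical because a CLAD-free patient can need a 20% fall while a patient with CLAD needs 15%. The documents do not support that. Onset and progression are different constructs, and nothing says that they must share a threshold. The comparison also takes the 15% rule as limited to patients with CLAD at entry, which the word progressive implies but the text does not state. Applied to everyone, the 15% rule would make the patient falling from 85% to 69% an event.

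A reader might also infer that the personal reference is plainly the right choice. It is not: it raises chance events near 80%, as the second table shows. Nor does it remove the difference between the two thresholds. Above r = 0.80/0.85 = 94.1%, a CLAD-free patient still needs more than a 15% fall.

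Finally, how many of the 40 patients would be reclassified is unknown, because the documents give no distribution of r. Study staff and those involved in care or testing are blinded (Section 5.2.5), so random misclassification should mainly dilute the comparison rather than favour an arm. Both points stand.

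**Conclusion.** The point holds as two gaps in the definition of the primary endpoint.

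First, the reference for the 80% rule is unnamed, and the choice matters most for patients who enter well below their best FEV1. At 85% of personal reference the fall required is 20% or 5.9%. For a patient at 100% the two readings agree. On the personal-reference reading there is also no FVC standard, so the FVC half of the rule cannot be derived, and a BOS 0 patient whose FVC is already low has no clear rule.

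Second, the progression rule as written accepts a single fall. The chance rate in stable patients is about 3-16% with six tests or 1.5-9% with three, and confirmation reduces it to at most 1.4%.

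The falls required are arithmetic, taking the 15% decrement as relative. The chance rates rest on the assumed CV, the number of tests and true stability, and are illustrations rather than forecasts. The documents do not show that the trial's result would change; they show that a small number of reclassified patients could change it.

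**What to change.** 1. In Section 4.10, require the 15% progression to be confirmed on two measurements at least 3 weeks apart. Date the event at the first, and allow the confirming test to fall after day 180. Spirometry is already planned to month 12 (Section 6.2).
2. Before unblinding, name one reference for the 80% rule, consistent with the BOS staging used at entry and defined for FVC as well as FEV1. Classify CLAD at entry by that same reference. Apply the new-CLAD rule to patients without CLAD at entry and the progression rule to the rest.
3. Repeat the primary analysis with the other reference as a sensitivity analysis.

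The cost is protocol wording and a derivation rule, with no added study visits. Confirmation will slightly lower the event count. If the personal reference is chosen, the plan should acknowledge the higher chance-event rate in patients just above 80% at entry, and that the 20% and 15% thresholds still differ for patients near their best FEV1.
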